A single (secondary endpoint) efficacy interim analysis is planned when approximately 60 subjects with an MRI-PDFF value of $\geq 8\%$ liver fat at Baseline have completed Week 26 or an Early Termination visit after Week 22. The purpose of the proposed interim analysis is to examine the TVB-2640 benefit over placebo based on a Week 26 secondary efficacy endpoint consisting of “proportion of MRI-PDFF $\geq 30\%$ responders, where an MRI-PDFF $\geq 30\%$ responder is defined as a subject with $\geq 8\%$ liver fat content at Baseline who achieves a percent change (reduction) from Baseline in MRI-PDFF $\geq 30\%$ ”. An interim analysis of the primary efficacy endpoint is not feasible since the primary endpoint is only evaluated at Week 52, and not Week 26. Therefore, a statistical penalty is not envisaged in conjunction with the Week 26 interim analysis of the above-stated secondary endpoint. Interim safety summaries will accompany the interim analysis of the secondary efficacy endpoint.

Planned study committees: An independent data monitoring committee (IDMC) will be established by charter to provide independent review and assessment of study data and to monitor the overall study conduct in a systematic manner to safeguard the safety of study subjects. The interim analysis will be reviewed by the IDMC and will include select biomarkers and safety interim results to allow for a more complete examination of the totality of the data.

Figure 1: Study Design

Abbreviations: CAP = controlled attenuation parameter; MRI = magnetic resonance imaging; NAS = nonalcoholic fatty liver disease activity score; NASH = nonalcoholic steatohepatitis; PDFF = protein density fat fraction; [REDACTED] PO = orally; QD = once daily.

Table 2: Schedule of Assessments

Evaluation		Study Visit									
Screening/Baseline Assessments											
Informed consent	X										
Inclusion and exclusion criteria review	X	X									
Demographics	X										
Pregnancy test ^b	X ^b	X ^b									
eGFR	X										
Medical and social history ^c	X	X									
Alcohol breath test or blood alcohol test	X	X									
Urine drug screen ^d	X	X									
Histologic confirmation of NASH diagnosis, and either Stage 2 or Stage 3 fibrosis ^e	X										
Aminotransferases and INR	X	X									
Viral serology ^f	X										
Genomics pertaining to NASH ^g		X									
Height, body weight, BMI, waist and hip circumference, and waist-hip ratio ^h	X	X									
Safety Assessments											
12-lead ECG ⁱ	X	X ^j				X			X		X
Vital signs ^k	X	X	X	X	X	X	X	X	X		X
Complete physical examination	X									X	X
Symptom-directed physical examination ^l		X	X	X	X	X	X	X			
Eye examination ^m		X ^m									
Safety laboratory tests											
Hematology and coagulation ⁿ	X	X	X	X	X	X	X	X	X	X	X

Evaluation												
Liver aminotransferases ^o	X	X	X	X	X	X	X	X	X	X		
Clinical chemistry ^p	X	X	X	X	X	X	X	X	X	X		
Urinalysis ^q	X	X	X	X	X	X	X	X	X	X		
Pregnancy testing ^b			X	X	X	X	X	X	X	X		
Adverse events ^{gg}			Document all AEs occurring from the signing of the ICF through 28 days after the last dose									
Prior/concomitant medications ^f	X		Document medications as described in Section 9.7									
Efficacy and PD Assessments												
Liver histology/NAS/digital pathology ^{es}	X ^e								X ^e	X ^e		
MRI-PDFF ^t	X ^t					X ^t			X ^t	X ^t		
FibroScan, FAST score, and CAP score ^u	X					X			X	X		
Body weight	X	X	X	X	X	X	X	X	X	X		
Waist and hip circumference and waist-hip ratio ^h	X	X							X	X		
Blood sample collection for:												
Lipid panel ^v	X	X	X	X	X	X	X	X	X	X		
HbA1c	X	X			X	X	X	X	X	X		
Metabolic panel ^w		X	X	X	X	X	X	X	X	X		
Fibrosis biomarkers ^x		X	X		X	X			X	X		
NASH inflammation and metabolic biomarkers ^y		X	X		X	X			X	X		
Alcohol biomarkers ^z		X				X			X	X		
Lipidomic biomarkers ^{aa}		X	X		X	X			X	X		
Lipoprotein analyses (subset of sites) ^{bb}		X				X			X	X		
Stool sample (subset of sites)		X				X			X	X		
Nutritional survey (subset of sites)		X				X			X	X		

		[REDACTED]							
		[REDACTED]	[REDACTED]	[REDACTED]	[REDACTED]	[REDACTED]	[REDACTED]	[REDACTED]	[REDACTED]
Evaluation									
Urine sample for storage ^{cc}		X						X	X
Whole blood sample for storage ^{cc}		X						X	X
[REDACTED]									
[REDACTED]		[REDACTED]	[REDACTED]					[REDACTED]	[REDACTED]
[REDACTED]		[REDACTED]	[REDACTED]					[REDACTED]	[REDACTED]
Study Drug Administration									
Randomization ^{ff}		X							
Dosing compliance (Diary)		X	X	X	X	X	X	X	X
Study drug dispensation ^{gg}		X			X	X	X		
Study drug administration ^{gg}		QD PO from Day 1 through Week 52							
Study drug accountability ^{gg}					X	X	X	X	X

Abbreviations: adipo-IR = adipose tissue insulin resistance index; ALP = alkaline phosphatase; ALT = alanine aminotransferase; ANC = absolute neutrophil count;

Abbreviations: ApoE = apolipoprotein E; ApoB = apolipoprotein B; aPTT = activated partial thromboplastin time; AST = aspartate aminotransferase; β -HCG = beta-human chorionic gonadotropin; BMI = body mass index; BUN = blood urea nitrogen; CAP = controlled attenuation parameter; CDT = carbohydrate-deficient transferrin; CK-18 = cytokeratin-18; COVID-19 = coronavirus disease-19; CPK = creatine phosphokinase; ECG = electrocardiogram; eGFR = estimated glomerular filtration rate; ELF = enhanced liver function (score); FAEE = fatty acid ethyl esters; FAST = FibroScan-AST; FGF-21 = fibroblast growth factor-21; FIB-4 = Fibrosis-4 score; FU = follow-up; GGT = gamma-glutamyltransferase; HA = hyaluronic acid; HbA1c = glycosylated hemoglobin; HBsAg = hepatitis B surface antigen; HCV = hepatitis C virus; HDL-C = high density lipoprotein cholesterol; HIV = human immunodeficiency virus; HOMA = homeostatic model assessment index; INR = international normalized ratio; IR = insulin resistance; LDL-C = low density lipoprotein cholesterol; Lp(a) = lipoprotein (a); MCHC = mean corpuscular hemoglobin concentration; MCV = mean corpuscular volume; MRI = magnetic resonance imaging; NAFLD: nonalcoholic fatty liver disease; NAS = nonalcoholic fatty liver disease activity score; NASH = nonalcoholic steatohepatitis; NEFA = nonesterified fatty acid; PCR = polymerase chain reaction; PD = pharmacodynamic; PDFF = proton density fat fraction; PEth = phosphatidylethanol; PIIINP = procollagen III amino-terminal peptide; [REDACTED] PO = orally; PRO-C3 = pro-peptide of type III collagen; PT = prothrombin time; QD = once daily; RBC = red blood cell; RNA: ribonucleic acid; SARS-CoV-2: severe acute respiratory syndrome- coronavirus -2 TIMP-1 = tissue inhibitor of matrix metalloproteinase 1; vLDL = very low density lipoprotein cholesterol; WBC = white blood cell.

- a. Baseline evaluations are to be performed predose, unless otherwise specified.
- b. Serum β -hCG pregnancy testing is to be performed for female subjects of childbearing potential during Screening, and a urine pregnancy test is to be performed within 24 hours before the first dose on Day 1 (Baseline). Subjects with a positive serum pregnancy test result are not eligible for study participation. Serum pregnancy testing is to be repeated at the Week 56 Follow-up visit or at Early Termination (whichever takes place sooner), and during the study any time pregnancy is suspected. Female subjects of childbearing potential are required to perform urine home pregnancy tests monthly between study visits and the results should be recorded in a subject diary. A positive urine test should be followed by an unscheduled serum pregnancy test as soon as possible. Study drug is to be held in the event of a positive urine pregnancy test and permanently discontinued for any subject with a positive serum pregnancy test result.
- c. A complete medical history is to be documented during Screening and updated at Baseline, prior to administration of the first study drug dose. A history of harmful alcohol intake for a period of more than 3 consecutive months within 1 year prior to Screening in the judgement of the Investigator is exclusionary.

- d. Active substance abuse, including inhaled or injected substances (cocaine and other illegal/banned substances; any opiate, amphetamine, or benzodiazepine for which the subject does not have an existing prescription), within 1 year prior to Screening is exclusionary. However, recreational cannabis/tetrahydrocannabinol use is permissible.
- e. To qualify for this study, liver histology results must be available before randomization (randomization is within 3 days of Baseline [Day 1]). If the subject terminates early from the study, the end of study biopsy is only required if the subject has completed at least 42 weeks of treatment. See Section 8.1, Criterion 7, and Section 8.2, Criterion 20 for detailed requirements for histology results.
- f. Screening serologies include HIV RNA, HBsAg, anti-HCV antibody, HCV RNA (reflex testing, if HCV antibody result at Screening is positive), and SARS-CoV-2 PCR test. The SARS-CoV-2 PCR test may be performed locally and must be performed within 30 days before Baseline (Day 1), other viral serology tests should be performed by the central laboratory. Subjects with chronic HCV infection and liver disease who were treated with anti-HCV therapy and achieved a sustained virologic response at least 2 years prior to Screening are not prevented from study participation.
- g. A blood sample for genomics pertaining to NASH will be collected at all sites unless forbidden by local regulations. If not collected at Baseline, this sample may be collected at any other time after the subject signs the separate consent for this sample. Provision of blood samples for genomic analysis is voluntary.
- h. Also see further information regarding anthropometric measurements in Section 12.1.6.
- i. Single 12-lead ECGs are to be performed at the times indicated and at any other time as clinically indicated. ECGs should be performed before any blood draws planned for the same time period.
- j. On Day 1, a single 12-lead ECG should be performed up to 2 hours before and 4 hours (-1 hour/+ 2 hours) after the first study drug dose.
- k. Vital signs include oral temperature, pulse, systolic/diastolic blood pressure, and respiration rate. Measurements are to be made after the subject has been resting in a supine position for a minimum of 5 minutes.
- l. Abbreviated, symptom-directed physical examinations will include at a minimum, examination of focused liver signs (e.g., jaundice, spider angioma, palmar erythema, hepatomegaly, splenomegaly, asterixis), skin, and extremities, and any other areas needed to address any complaints or concerns verbalized by the subject. If hand-foot symptoms/signs present at this visit or previous hand-foot symptoms/signs increases in severity to a Grade 2 or above, a dermatologist consult should be considered for further evaluation and treatment recommendations.
- m. Baseline eye examinations may be performed at any time during the Screening period. Eye exams at Week 4, Week 8, Week 13, Week 26, Week 39, Week 52, Week 56 and/or Early Termination are required only if eye-related signs or symptoms are reported by the subject or observed by the investigator. If a subject experiences a treatment-emergent eye abnormality, an eye examination inclusive of slit lamp and near and far visual acuity testing should be performed by a qualified ophthalmologist or optometrist within 24 to 48 hours of event onset or on the next business day after symptom onset to evaluate the abnormality.
- n. Hematology and coagulation parameters include hemoglobin, MCV, MCHC, hematocrit, platelet count, RBC count, WBC count with differential, ANC, and PT, aPTT, INR, and fibrinogen. See also [Table 5](#).
- o. Liver aminotransferases include AST and ALT. Liver aminotransferases collected as part of the clinical chemistry panel for safety are also applicable for efficacy assessments.
- p. Fasting clinical chemistries include chloride, carbon dioxide, sodium, potassium, glucose, BUN, calcium, magnesium, creatinine, albumin, ALT, AST, ALP, GGT, total bilirubin, indirect and direct bilirubin, and total protein. CPK (total and fractionated) is to be reported at Screening and at Baseline. See also [Table 5](#).
- q. Urinalysis includes specific gravity, pH, blood, glucose, protein, ketones, and microscopic examination of sediment, if present. See also [Table 5](#).
- r. Subject contact to reliably assess medication use between visits is encouraged around Week 10, Week 17, Week 23, Week 30, Week 34, Week 43, and Week 47. See Section 9.7 for a list of accepted and excluded concomitant medications. If a subject receives a vaccine, including the COVID-19 vaccine, details regarding that vaccine should be recorded as a concomitant medication(s), including manufacturer, dose, and dates of each injection. Any vaccine-related reactions should be recorded as described in Section 12.2.
- s. The same biopsy samples will be used for histology analysis by the central study pathologist and by digital pathology.
- t. Subjects will have an MRI-PDFF performed at each indicated timepoint unless it presents a logistical or physical hardship to the subject. MRI-PDFF will not be performed at select sites. The Baseline MRI-PDFF is to be performed during Screening or at Baseline before study drug dosing on Day 1. MRI-PDFF is not required at Early Termination if a subject has completed less than 22 weeks of study treatment.
- u. CAP and FAST scores will be measured each time a FibroScan is performed (unless the enrolling study site does not have the capability to measure CAP).
- v. Fasting lipid panel includes LDL-C, vLDL, HDL-C, non-HDL-C, total cholesterol, triglycerides, ApoB, and Lp(a) particles.
- w. Fasting metabolic panel includes insulin and NEFA. HOMA-IR and adipo-IR are to be calculated from fasting insulin, fasting glucose (see footnote p), and fasting NEFA, as applicable. An analysis of bile acid will also be performed at Baseline, Week 26, Week 52, and/or at Early Termination.

- x. Fibrosis biomarkers include ELF (TIMP-1, PIIINP, and HA), PRO-C3, FIB-4, and potentially other markers.
- y. NASH biomarkers include CK-18, adiponectin, FGF-21, and other chemokines/cytokines relevant to NASH.
- z. Alcohol biomarkers will include PEth and may also include: GGT, MCV, ALT/AST, CDT, and FAEE.
- aa. Blood samples for lipidomic biomarkers will be collected in all subjects and analysis will include tripalmitin, ceramides, bile acids, diacylglycerols, and other classes of metabolites.
- bb. The lipoprotein substudy will be conducted in approximately 30 or more subjects. Provision of blood samples for the lipoprotein substudy is voluntary.
- cc. Additional spot urine and blood samples will be collected at specified time points and stored for potential future analyses for biomarkers relevant to NAFLD/NASH. These samples will not be used for genetic analysis or for creation of cell lines. Providing spot urine and blood samples for storage is voluntary.
- dd. [REDACTED]
- ee. [REDACTED]
- ff. [REDACTED]
- gg. In the event a subject is unable to complete the end of treatment MRI-PDFF and/or liver biopsy within the protocol-specified window (Week 52 +/- one week), extended dosing is permitted to maintain continuous dosing up to the time both assessments are completed, to a maximum total of 56 weeks of dosing. In this instance, the Follow-up visit at Week 56 for posttreatment safety and efficacy assessments is to be adjusted to occur four weeks after the last dose (+/- one week).

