Baseline (and percent change from Baseline) as the dependent variable; treatment group, T2DM status (yes or no), region (North America or not North America), and amount of fibrosis (F2 or F3) as factors; and Baseline as a covariate. Least-squares means and their differences will be estimated from the ANCOVA model and their corresponding 95% CI will be derived. Inferential statistics will be presented for both the ANCOVA model and the Wilcoxon test. For the continuous secondary endpoints with sufficient postbaseline frequency of measurements, a mixed model repeated measure (MMRM) model will also be employed.

Analysis of PK parameters: Planned PK parameters will be calculated for each subject with serial PK samples employing the standard linear trapezoidal convention using all available drug concentration measurements. Specifically, the following TVB-2640 PK parameters will be estimated (via noncompartmental methods): time to maximum concentration (T_{max}), maximum concentration (C_{max}), area under the concentration-time curve from time of dosing to the last measured concentration ($AUC_{0-\text{last}}$), area under the concentration-time curve from time of dosing extrapolated to infinity ($AUC_{0-\infty}$), and plasma elimination half-life ($t_{1/2}$). Standard descriptive statistics (mean, median, n, standard deviation, minimum, maximum, coefficient of variation) will be used to summarize the stated PK parameters along with the corresponding 90% CI whenever appropriate. All subject-level concentrations will be provided in a listing and the stated summary statistics presented in a tabular format. Graphical depiction of the concentration measurements by time profile will be presented. Sparse PK sample results will be analyzed using a population PK model.

Definition of analysis populations:

- Intention-to-Treat (ITT) population: Comprises all randomized subjects; this population will serve as the basis for all efficacy analyses. Subjects' data will be analyzed according to their randomized treatment assignment.
- Modified Intention-to-Treat (mITT): Comprises all subjects in the ITT population who have completed at least 42 weeks of treatment and have an evaluable posttreatment histological assessment.

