13. STATISTICAL CONSIDERATIONS

13.1. Statistical General Considerations

This is a multi-center, randomized, double-blind, placebo-controlled, parallel-design study to evaluate the safety and efficacy of TVB-2640 compared with matching placebo in subjects with NASH.

For “change from Baseline” and “percent change from Baseline” calculations, “Baseline” refers to the last measurement obtained prior to the first administration of study drug. Study Day 1 is the first day of study treatment (TVB-2640 50 mg or placebo). Demographic data (including age, race, ethnicity, sex, height, and weight), medical history, prior treatments, pretreatment clinical characteristics, and other baseline characteristics will be summarized by treatment group and overall.

Descriptive statistics will be displayed by treatment group for all subjects with liver fibrosis stage F2-F3, for all subjects with liver fibrosis stage F1-F3, and for all subjects, as appropriate, to provide an overview of the study results. As appropriate, descriptive statistics will also be displayed by treatment group and by enrollment group. For categorical parameters, the number and percentage of subjects in each category will be presented in data summaries. The denominators for percentages will be based on the number of subjects (n) appropriate for analysis. Continuous variables will generally be summarized based on the following: n, mean, standard deviation, median, minimum, maximum, and standard error of the mean. Categorical data will be summarized using frequency tabulations (number and percentage of subjects).

Demographics and Baseline characteristics (medical histories, physical examinations, and concomitant medications) will be summarized using descriptive statistics for continuous variables and frequency distributions for discrete variables. Study subjects who discontinue the study along with reasons for discontinuation will be summarized and listed. Confidence intervals will be at the 90% and 95% levels. All statistical analyses will be performed using SAS v9.4.

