APPENDIX A. ALGORITHM FOR EVALUATING SUBJECTS FOR POTENTIAL DRUG-INDUCED LIVER INJURY

During the study, aminotransferase elevations are to be managed as follows:

1. Isolated aminotransferase elevation (i.e., total bilirubin - normal):

ALT or AST	Event during the study	Action
Baseline ALT and AST within normal range	Increase $\geq 5 \times$ ULN	Repeat liver profile (AST, ALT, bilirubin) and PT/INR within 2 to 3 business days from the date results are received for review. Monitor the subject as per “close observation” definition* in the DILI guidance.
ALT or AST above normal range at Baseline	Increase $\geq 3 \times$ Baseline result, but no liver related symptoms (e.g., anorexia, nausea, vomiting, right upper quadrant pain, pruritus, cholestasis)	Interrupt study drug for at least 15 days. Initiate potential DILI evaluation for alternative etiologies, and repeat liver profile and PT/INR within 2 to 3 business days from the date results are received for review, and place subject under “close observation” as defined in the DILI guidance.
ALT or AST above normal range at Baseline	Increase $\geq 3 \times$ Baseline result, and subject experiences liver- related symptoms (e.g., anorexia, nausea, vomiting, right upper quadrant pain, pruritus, cholestasis)	Interrupt study drug for at least 15 days. Initiate potential DILI evaluation for alternative etiologies, and repeat liver profile and PT/INR within 2 to 3 business days from the date results are received for review, and place subject under “close observation” as defined in the DILI guidance.

Abbreviations: ALP = alkaline phosphatase; ALT = alanine aminotransferase; AST = aspartate aminotransferase; DILI = drug-induced liver injury; GGT = gamma-glutamyltransferase; INR = international normalized ratio; PT = prothrombin time; ULN = upper limit of normal.

*Close observation as defined in the FDA DILI guidance (i.e., laboratory testing and physical examination 2 to 3 times per week. Study drug is to be restarted only if a firm alternative etiology is “identified” and the liver tests return to ‘baseline’ levels).

Note the following:

The ‘baseline’ result for any laboratory parameter is the average of the Screening visit result, the Day 1 visit result and any unscheduled visit that occurred during the Screening period.’

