7.6. Baseline and Post-Baseline Changes

Unless stated otherwise, baseline will be based on the last non-missing value collected prior to the start of study treatment based on the treatment start date and time, if applicable. Post-baseline values will be those collected after the treatment start date and time, if applicable.

Change from baseline is defined as: post-baseline value – baseline value.

Percentage change from baseline is defined as: $(\text{post-baseline value} - \text{baseline value})/\text{baseline value} \times 100\%$.

7.7. Handling Below Limit of Quantification (BLQ) or Lower Limit of Quantification (LLOQ) Values

Any parameters with values identified as $<x$, $\leq x$, $>x$, or $\geq x$ will be analyzed using the ‘x’ value (the analysis will ignore the $<$, \leq , $>$, or \geq symbol).

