9.2. Secondary Efficacy Endpoints and Analyses

Secondary efficacy analyses for the other histological responder endpoints will be analyzed in the ITT and mITT populations using the methods described for the primary efficacy endpoint.

Secondary efficacy analyses of endpoints expressed as percent change or change from Baseline only at Week 26 or only at Week 52 will be analyzed in the ITT analysis set using an analysis of covariance (ANCOVA) model with fixed effects for T2DM status at baseline (Yes, No) and treatment group, and a covariate term for baseline analysis value of response. Least squares (LS) means for the percent change from Baseline by treatment and the associated standard errors, the

LS means for the difference between treatment groups, and the associated two-sided 95% CIs and two-sided p-values, based on t-tests, will be derived from the ANCOVA model.

For secondary endpoints assessed at multiple visits, a linear mixed-effects model for repeated measures (MMRM) may be used. The model will include T2DM status at baseline (Yes, No), treatment group, visit, and treatment-by-visit interaction as the fixed effects, and baseline value as a covariate, and the model will use an unstructured variance-covariance matrix. The point estimates for the least-squares mean of the difference treatment groups at each visit and the corresponding 95% confidence interval and two-sided p-value will be summarized. If convergence problems arise when fitting the model, a spatial power covariance structure will be used as a first step. If the model still has convergence issues, compound symmetry covariance structure will be employed. The Kenward-Roger correction for the denominator degrees of freedom will be applied.

ALT, AST, ALP, and GGT will also be summarized in shift tables of baseline to each visit based on range categories of low (below lower limit of normal [LLN], normal, and high [above upper limit of normal [ULN]]).

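### Endpoints 16, 17 and the glucose and HbA1c parts of 19 adjust for one pre-treatment value although Screening supplies a second; using both is a cheap, optional gain in precision

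*Protocol*

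**What the plan says.** Both documents define Baseline as one measurement. Protocol 13.1 says that it "refers to the last measurement obtained prior to the first administration of study drug". SAP 7.6 says that "baseline will be based on the last non-missing value collected prior to the start of study treatment".

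The models use that one value of the outcome:

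- The Protocol ANCOVA (Synopsis and 13.2.2) has treatment, T2DM status, region "and amount of fibrosis (F2 or F3) as factors; and Baseline as a covariate".
- The SAP 9.2 ANCOVA has treatment and T2DM status "and a covariate term for baseline analysis value of response".
- The SAP 9.2 MMRM has T2DM status, treatment, visit and treatment-by-visit, "and baseline value as a covariate, and the model will use an unstructured variance-covariance matrix".

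In Table 2 of the Protocol, the rows for clinical chemistry, liver aminotransferases, lipid panel and HbA1c are marked in both of the first two visit columns. The Screening/Baseline block does the same for "Aminotransferases and INR". Footnote p places glucose, ALT, AST, ALP and GGT in the fasting chemistry panel.

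Appendix A uses a different laboratory baseline for the liver-injury algorithm: it "is the average of the Screening visit result, the Day 1 visit result" and any unscheduled result from the Screening period.

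**The concern.** A single ALT, triglyceride or glucose value carries within-subject variation as well as the subject's underlying level. A second reading taken before randomisation therefore usually says something more about that level, and about where the subject would be at Week 52 without treatment. Entering it as a further covariate leaves the estimand unchanged and introduces no bias, because it precedes randomisation.

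Here that second reading is scheduled for every subject and its cost is already paid. If it predicts Week 52 beyond Day 1, the planned standard errors for endpoints 16, 17 and part of 19 are larger than they need be. The placebo arm has only about 54 subjects, and no power is stated for these endpoints.

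**Working it through.** **Is the second value really there?** The visit headings of Table 2 do not survive in the copy reviewed, so I checked the first column against the text. Protocol 8.2 applies Screening limits to HbA1c (exclusion 10), LDL-C (11), ALT and AST (12) and ALP (13). GGT and glucose belong to the same chemistry panel as ALT and AST. Insulin and NEFA, and hence HOMA-IR and adipo-IR, have no Screening mark. ALP is named among the secondary endpoints only in the SAP.

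**The plan's own figure.** The only stated calculation is for the binary primary endpoint (Protocol 13.5, SAP 4.3): 40% versus 20%, one-sided 0.05, 80% power, 2:1 allocation, 18.5% dropout. With unpooled variance, placebo n = (0.2×0.8 + 0.4×0.6/2) × (1.645 + 0.842)² / 0.2² = 43.3, so 44. The total is 44 + 88 = 132, and 132/0.815 = 162. It reproduces. It says nothing about the continuous endpoints, but it supplies 88 and 44 as plausible completer numbers.

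**Formulae.** Let rB and rS be the correlations of the Day 1 and Screening values with Week 52, and ρ the correlation between Day 1 and Screening. As a fraction of outcome variance, the residual variance is:

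- one baseline: 1 − rB². With Day 1 as a covariate, analysing change or the raw value gives the same treatment contrast.
- two baselines: 1 − (rB² + rS² − 2·rB·rS·ρ)/(1 − ρ²). When rB = rS = r this is 1 − 2r²/(1 + ρ).

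For a contrast that has 80% power (two-sided 0.05) with one baseline, power with two is Φ[(1.960 + 0.842)/√v − 1.960], where v is the ratio of the two residual variances.

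**Results.** All correlations are assumptions.

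| rB | rS | ρ | one baseline | two baselines | reduction | power |
|---|---|---|---|---|---|---|
| 0.7 | 0.7 | 0.7 | 0.510 | 0.424 | 17.0% | 86.7% |
| 0.6 | 0.6 | 0.6 | 0.640 | 0.550 | 14.1% | 85.6% |
| 0.5 | 0.5 | 0.5 | 0.750 | 0.667 | 11.1% | 84.4% |
| 0.6 | 0.6 | 0.75 | 0.640 | 0.589 | 8.0% | 83.2% |
| 0.6 | 0.6 | 0.85 | 0.640 | 0.611 | 4.6% | 81.8% |
| 0.5 | 0.5 | 0.8 | 0.750 | 0.722 | 3.7% | 81.5% |
| 0.6 | 0.55 | 0.8 | 0.640 | 0.626 | 2.1% | 80.8% |
| 0.6 | 0.5 | 0.8 | 0.640 | 0.639 | 0.2% | 80.1% |
| 0.6 | 0.48 | 0.8 | 0.640 | 0.640 | 0.0% | 80.0% |

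The last row is the limiting case rS = ρ·rB (0.8 × 0.6 = 0.48), where Screening adds nothing beyond Day 1. Intermediate assumptions fill the gap between the bands: (0.6, 0.6, 0.7) gives 9.9% and (0.7, 0.7, 0.8) gives 10.7%. In the three equal-correlation rows, 132 completers carry the information of about 148, 154 and 159.

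**A form of the fix that backfires.** Suppose the covariate becomes the mean of Screening and Day 1 while the outcome stays change from Day 1. With all correlations 0.7, the change has variance 2 − 1.4 = 0.6, its covariance with the mean is 0.7 − 0.85 = −0.15, and the mean has variance 0.85. The residual is 0.6 − 0.0225/0.85 = 0.574, worse than the 0.510 of the planned model. The two values should enter as separate covariates.

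**The case against.** The strongest reply is that the gain is unproven. Screening may precede randomisation by up to 90 days, and eligibility limits truncate Screening ALT, AST, ALP, LDL-C and HbA1c. Repeat tests may also replace a failing result. Each of these can make Screening the weaker predictor. This stands, and it is why the range must begin at about 0%. A reader might infer a guaranteed minimum gain from the equal-correlation rows alone; nothing in the documents supports one.

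Second, the formula describes an ANCOVA at one visit. SAP 9.2 keeps ANCOVA for endpoints assessed only at Week 26 or only at Week 52, whereas endpoints 16, 17 and 19 are assessed at every visit and so point to the MMRM. T2DM status is already in the model and may overlap with glucose and HbA1c. Percent change was not examined. This also stands: the figures are a guide, not an MMRM result.

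Third, a second covariate has a cost. Under ordinary complete-case fitting, a subject without a Screening value would drop out. If Day 1 is missing, Baseline falls back to an earlier value under SAP 7.6, and the two covariates could be the same measurement. Both problems are real, and both are removed by one stated rule.

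Fourth, Appendix A might be read as showing that the plan contradicts itself. It does not: its average serves action thresholds for individual subjects, not a comparison between groups.

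**Conclusion.** The point holds as an inexpensive efficiency improvement, optional in priority. For the listed analytes the models use one pre-treatment value of the outcome although two are scheduled. Adding the second could reduce residual variance by about 0% if Screening adds nothing, by about 2% to 8% if the two pre-treatment values correlate more with each other than with Week 52, and by about 11% to 17% if all correlations are equal at 0.5 to 0.7. The corresponding power for a hypothetical 80% contrast is about 80% to 87%. All of this rests on assumed correlations and a single-visit model.

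A reader might go further and conclude that the planned analysis is biased or incorrect, or that the trial is underpowered as a result. The documents support neither. Adjusting for one baseline value is valid. These secondary endpoints carry no power target, and SAP 7.3 gives them no multiplicity control. The primary CMH analysis and N = 162 do not involve these values, and the Protocol's Wilcoxon tests have no covariates and would not change.

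**What to change.** Before unblinding, amend SAP 9.2, and for consistency Protocol 13.2.2 and the Synopsis, for endpoints 16, 17 and the glucose and HbA1c parts of 19:

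1. Add the last Screening value as a second covariate in the ANCOVA and the MMRM, defined as the latest pre-treatment value that is not itself the Baseline value.
2. Keep change from Baseline calculated from the Baseline value of SAP 7.6.
3. State that a subject with only one pre-treatment value stays in the model, for example by a single imputation of the missing covariate from the available one, done without reference to treatment.

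Insulin, NEFA, HOMA-IR and adipo-IR stay as planned. The change needs no new visit or sample. It costs one degree of freedom and a small amount of programming.
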